#### 6.5.2.12 *Drug-induced Liver Injury*

The potential for drug-induced liver injury will be monitored using assessments of liver function via serum chemistry at regular intervals. Laboratory values consistent with Hy's Law criteria will be used to indicate the potential for drug-induced liver injury (ie, all 3 of the following must coexist):

- 1) ALT or AST  $\geq 3 \times$  upper limit of normal (ULN)
- 2) Total bilirubin  $\geq 2 \times$  ULN
- 3) ALP  $< 2 \times$  ULN

Should the laboratory parameters suggesting drug-induced liver injury be observed, other potential causative factors may be investigated (eg, viral hepatitis A, HBV, or HCV; preexisting or acute liver disease; or another drug capable of causing the observed injury).

### 6.5.2.13 *Laboratory Assessments for Cytokine Release Syndrome*

Blood (plasma) samples will be collected at Screening and as clinically indicated for assessment of interferon gamma (IFN- $\gamma$ ), interleukin 6 (IL-6), IL-1, tumor necrosis factor alpha (TNF- $\alpha$ ), C-reactive protein, and ferritin. If CRS is suspected, a blood (plasma) sample will be collected within 5 hours (or as soon as possible) after occurrence of the event, and 1 week after occurrence of the event.

### 6.5.2.14 *Pregnancy Testing and Contraception Requirements*

For study eligibility, women of childbearing potential must have a negative serum pregnancy test at Screening and within 24 hours prior to first dose of study drug. A urine pregnancy test may be performed at all other indicated visits. In case of delayed menstrual period (> 1 month), absence of pregnancy will be confirmed prior to next dose of study drug or next study visit, whichever occurs first. If a urine pregnancy test is positive, the results will be confirmed with a serum pregnancy test. Pregnancy of a subject or partner will be reported and followed.

### 6.5.2.15 *Exploratory Safety Variables*

Exploratory safety endpoints include the following:

- Changes from baseline in selected protein, cellular, and genomic expression parameters from blood and tissue samples; prognostic and/or predictive value
- Exploration of individual subject deoxyribonucleic acid (DNA) sequence variations (eg, single nucleotide polymorphisms [SNPs]) and relationship with safety, tolerability, and clinical benefit

## 6.5.3 *Description of Pharmacokinetic Variables*

Blood samples will be obtained at time points specified in [Table 2](#) to characterize the plasma concentrations of ADU-S100 when administered with pembrolizumab after a single dose (Cycle 1 Day 1) and after repeat dosing (Cycle 1 Day 8 and Cycle 2 Day 1).

**Table 2 ADU-S100 PK Sampling Schedule**

CYCLE	DAY	SCHEDULED TIME (Sampling Window) 
Cycle 1	1	Pre-dose (within 60 min prior to ADU-S100 dosing) Post-dose: 1 h ( $\pm$ 15 min), and 2 h ( $\pm$ 15 min)
	8	Pre-dose (within 60 min prior to ADU-S100 dosing) Post-dose: 1 h ( $\pm$ 15 min), and 2 h ( $\pm$ 15 min)
Cycle 2	1	Pre-dose (within 60 min prior to ADU-S100 dosing) Post-dose: 1 h ( $\pm$ 15 min), and 2 h ( $\pm$ 15 min)

 Post-dose is defined as time from completion of first ADU-S100 intratumoral injection.

The time points specified in Table 2 are applicable to subjects who consented under Protocol Amendment 3 or beyond. Subjects who consented under Protocol Amendment 1 will have the following post-dose sampling time points: 2 min ( $\pm 2$  min), 15 min ( $\pm 2$  min), 30 min ( $\pm 5$  min), 1 h ( $\pm 5$  min), and 2 h ( $\pm 10$  min). Subjects who consented under Protocol Amendment 2 will have the following post-dose sampling time points: approximately 2 min, approximately 15 min, 30 min ( $\pm 5$  min), 1 h ( $\pm 5$  min), and 2 h ( $\pm 10$  min).

When feasible, the following PK parameters will be estimated by non-compartmental methods using actual elapsed time from dosing:

- $AUC_{0-last}$ : Area under the concentration-time curve  $\langle \text{insert unit as concentration unit} \times \text{hours} \rangle$  ( $\text{h} \times \text{ng/mL}$ ) from time zero (pre-dose) to the last measureable concentration, calculated by the linear trapezoidal rule;
- $C_{max}$ : Maximum concentration  $\langle \text{insert unit} \rangle$  ( $\text{ng/mL}$ ), obtained directly from the observed concentration versus time data;

For calculations using the linear trapezoidal rule, the following formula will be used:

$$AUC = \frac{1}{2} (C_1 + C_2)(t_2 - t_1)$$

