#### ***CMIW815X2101/ADU-CL-07***

A total of 47 subjects have been treated with ADU-S100 at doses ranging from 50 to 6400 mcg and evaluated for dose-limiting toxicity (DLT) in the first in human study. Following intratumoral dose administration, ADU-S100 exhibits rapid absorption in the plasma, with  $C_{max}$  achieved right after injection in most subjects. ADU-S100 showed fast clearance in plasma, with mean apparent clearance (CL/F) ranging from 55.9 to 275 L/h and mean elimination  $t_{1/2}$  of approximately 10 to 23 minutes across the dose range of 50 to 6400 mcg. Inter-subject exposure variability was high and exposure of ADU-S100 generally increased with doses increasing from 50 to 6400 mcg.

One DLT has been reported at 6400  $\mu$ g (injection site ulcer). TEAEs, all grades, suspected to be related to study drug, were reported in 36 subjects (76.6%) overall. To date, the most frequently

reported AEs (>10% of subjects) include pyrexia (8 subjects, 17.0%), chills and injection site pain (7 subjects, 14.9%) and headache (6 subjects, 12.8%). Five subjects experienced Grade 3 events including injection site reaction and lipase increased (2 subjects, 4.3%), injection site ulcer, amylase increased, tumor pain and dyspnea (1 subject, 2.1%). One subject experienced a Grade 4 event, respiratory failure (2.1%). No clinically relevant changes of vital and ECG-parameters were observed.

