#### **7.4.8 Pharmacokinetic Analysis**

Pharmacokinetic parameters will be analyzed based on the All Treated Population. For each subject, the PK parameters described in [Section 6.5.3](#) will be determined by a non-compartmental approach when feasible. For the purpose of the non-compartmental PK analysis, all plasma concentration BLQ values occurring prior to the first measurable concentration will be set to zero. BLQ values occurring after the first measurable plasma concentration will be set to missing.

PK parameters will be summarized for the All Treated Population using descriptive statistics that includes the CV. Summaries of  $C_{\max}$  and AUC will also include point estimates for the geometric mean and geometric CV. The geometric mean is calculated by computing the mean of the log-transformed concentration values and then presented in the original scale by calculating the anti-log of the mean result. The geometric CV is calculated as  $100 \cdot \sqrt{\exp(\sigma^2) - 1}$ , where  $\sigma^2$  is the variance of the log-transformed data. Listings of calculated PK parameters will be provided.

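### The SAP pools Cmax and AUC over subjects first sampled at about 2 minutes and subjects first sampled at 1 hour, so the summary mixes a several-fold sampling artefact with exposure

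*SAP*

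**What the plan says.** SAP 6.5.3 ties the sampling times to the amendment under which a subject consented.

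- Amendment 1: "Subjects who consented under Protocol Amendment 1 will have the following post-dose sampling time points: 2 min", followed by 15 min, 30 min, 1 h and 2 h.
- Amendment 2: "Subjects who consented under Protocol Amendment 2 will have the following post-dose sampling time points: approximately 2 min, approximately 15 min, 30 min", followed by 1 h and 2 h.
- Amendment 3 or later: "The time points specified in Table 2 are applicable to subjects who consented under Protocol Amendment 3 or beyond". Table 2 lists a pre-dose sample, 1 h (±15 min) and 2 h (±15 min).

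The same section defines Cmax as the highest observed concentration and AUC0-last as linear trapezoids from pre-dose to the last measurable value. Both are derived where feasible; the term is not defined.

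SAP 7.4.8 states that "PK parameters will be summarized for the All Treated Population using descriptive statistics that includes the CV", and adds the geometric mean and geometric CV for Cmax and AUC. SAP 7.2 defines the All Treated Population as every subject who received any study drug. Nothing splits or restricts the parameter summary by schedule. Raw concentrations are handled differently: SAP 7.4.7 summarises them by sampling time point.

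Protocol 5.2.2, on the first-in-human study, says Cmax was "achieved right after injection in most subjects", gives a mean elimination half-life of "approximately 10 to 23 minutes across the dose range of 50 to 6400 mcg", and notes that "Inter-subject exposure variability was high".

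**The concern.** An observed maximum estimates the peak only if a sample is taken near the peak. On the early schedules the first sample comes about 2 minutes after injection. On the late schedule it comes nominally 60 minutes after, which is 2.6 to 6 half-lives past an immediate peak. The late-schedule value is a residual carrying the same label. AUC0-last has a related fault: one straight line from a pre-dose zero to the 1 h point replaces the whole early curve.

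Combining the two kinds of value gives a mean that moves with the number of subjects enrolled under each amendment. It also gives a CV containing a component that has nothing to do with how subjects handle the drug. A reader of the study report could take both as describing exposure to intratumoral ADU-S100 given with pembrolizumab.

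**Working it through.** Neither document states an expected Cmax or AUC, so there is no planned figure to reproduce. The check takes one subject with one true exposure and applies each schedule.

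**Inputs.** Half-life h from 10 to 23 min and an immediate peak (Protocol 5.2.2); nominal times and the ±15 min window (SAP 6.5.3); pre-dose concentration of zero (assumed). Assumed model: C(t) = 2^(−t/h), relative to the initial peak.

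**Cmax.** The late-schedule value relative to the 2-minute value is 2^(−(60−2)/h).

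- h = 10: 2^(−58/10) = 0.018, a 56-fold gap.
- h = 23: 2^(−58/23) = 0.174, a 5.7-fold gap.
- Using the window: a sample at 75 min with h = 10 gives 2^(−73/10) = 0.006; a sample at 45 min with h = 23 gives 2^(−43/23) = 0.27.

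**AUC0-last.** Sum of (C1 + C2)/2 × (t2 − t1), in units of peak × minutes:

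| Interval (min) | h = 10 | h = 23 |
|---|---|---|
| 0–2 | 0.87 | 0.94 |
| 2–15 | 7.96 | 10.26 |
| 15–30 | 3.59 | 7.81 |
| 30–60 | 2.11 | 8.53 |
| 60–120 | 0.48 | 5.73 |
| **Early schedule, total** | **15.00** | **33.27** |
| Late schedule, 0–60 | 0.47 | 4.92 |
| Late schedule, 60–120 | 0.48 | 5.73 |
| **Late schedule, total** | **0.94** | **10.65** |
| Ratio, early to late | 15.9 | 3.1 |

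The true AUC is h/ln 2, which is 14.4 and 33.2. The early schedule recovers 104% and 100% of it; the late schedule recovers 7% and 32%. If the 2 h value is below the quantification limit, SAP 7.4.8 sets it to missing. With that value lost on both schedules, the ratio becomes (15.00 − 0.48)/0.47, about 31, and (33.27 − 5.73)/4.92, about 5.6.

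**Absorption.** With an assumed first-order absorption half-life of 1 to 5 min instead of an instantaneous peak, the Cmax gap is 3.1- to 40-fold and the AUC gap 2.4- to 13.9-fold.

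**Effect on the pooled summary.** The split between schedules is not given, so the late-schedule share s is assumed. With no true difference between subjects, the pooled geometric mean Cmax relative to the 2-minute value is r^s, where r is the ratio above. The geometric CV is 100 × sqrt(exp(s(1−s)L²) − 1), where L = ln(1/r) is 4.02 for h = 10 and 1.75 for h = 23.

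| s | Pooled geometric mean, h = 10 to 23 | Geometric CV from schedule alone, h = 23 to 10 |
|---|---|---|
| 0.25 | 37% to 65% | 88% to 444% |
| 0.50 | 13% to 42% | 107% to 747% |
| 0.75 | 5% to 27% | 88% to 444% |

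**The case against.** The main objection is that little hangs on this. Protocol Section 6 marks the PK objective as removed by amendment, 10.4.3 stops sample collection, and Sections 12 and 12.7 place available PK data outside the protocol and its SAP. This stands, and it sets the priority. It does not dispose of the point: SAP 5.2 and 6.5.1.2 still list PK, 6.5.3 and 7.4.8 still specify the pooled summary, SAP 7.6 does not withdraw it, and samples taken before Amendment 4 remain to be analysed somewhere.

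A second objection is that derivation is required only where feasible. An observed maximum can be computed from any measurable sample, so without a definition tied to the schedule the qualifier does not exclude late-schedule subjects.

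Third, the size rests on a simple model and on a half-life from another study, reported as a range of means over 50 to 6400 mcg with no value at this trial's dose. Time also runs from the end of the first injection, and up to two lesions may be injected, so a second lesion's peak lies closer to the 1 h sample. These points can narrow the gap. The ±15 min window does too: at 45 min and a 23 min half-life, 45/23 = 1.96 half-lives have passed, so 2.6 is not a lower bound. A several-fold gap remains over the range checked.

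A reader might also infer that comparisons of single with repeat dosing are invalid. The documents do not support this. Schedule follows the amendment at consent, and Table 2 uses the same times on all three PK days, so a within-subject ratio is not confounded by amendment. On the late schedule such a ratio may still be noisy, because moving a sample from 45 to 75 min changes it 2.5-fold (2^(30/23)) to 8-fold (2^(30/10)). Neither document plans a comparison with other studies.

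**Conclusion.** The point holds. As written, the SAP would summarise near-peak values and late residuals as one parameter. For the same true exposure, the late-schedule Cmax is about 2 to 17% of the 2-minute value at nominal times, or about 0.6 to 27% with the ±15 min window on the 1 h sample. AUC0-last differs about 3- to 16-fold. These figures assume mono-exponential decline from injection and that the earlier study's half-life applies here.

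It would go too far to say that the pooled figures carry no information about exposure. They mix exposure with sampling, and true between-subject variability is reported as high but not quantified. The effect on the pooled mean and CV cannot be fixed without the split between schedules. If all PK subjects share one schedule, nothing is mixed, although Cmax from the late schedule alone would still miss the peak. Raw concentrations are unaffected by this pooling, being summarised by time point. Priority is low, because no decision in the trial rests on Cmax or AUC.

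**What to change.** Define feasibility by schedule. Derive and summarise Cmax and AUC0-last only for subjects with the 2 to 30 minute samples (Amendments 1 and 2). For subjects under Amendment 3 or later, report the 1 h and 2 h concentrations only, as SAP 7.4.7 already allows. Do not pool parameters across schedules, and state the number of subjects on each.

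Because the current protocol places available PK outside the SAP, put this rule in the separate PK document, or delete 6.5.3, 7.4.7 and 7.4.8 from the SAP. If the sections are deleted, the PK entries in SAP 5.2 and 6.5.1.2 should be aligned and the change recorded in 7.6.

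The cost is wording, plus fewer subjects contributing to Cmax and AUC. No new data are needed.

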#### 6.5.4 Biomarker Assessments

Whole blood, plasma, and tumor tissue will be collected from all enrolled subjects (where not prohibited by local regulations or policies). The results may help to inform dose selection, monitor baseline and post-treatment immune responses; and possibly further characterize the mechanism of action and/or determine potential prognostic and/or predictive biomarkers.

#### 6.6 Data Quality Assurance

Report summaries will be generated using validated Base SAS® software, version 9.4 or higher, on a PC or server-based platform. Additional validated software may be used to generate analyses, as needed.

All SAS programs that create outputs or supporting analysis datasets will be validated by a second statistical programmer or biostatistician. At a minimum, validation of programs will consist of a review of the program log, review of output or dataset format and structure, and independent confirmatory programming to verify output results or dataset content. Additionally, all outputs will undergo a review by a senior level team member before finalization.

The content of the source data will be reviewed on an ongoing basis by project statistical programmers and statisticians. Data will be checked for missing values, invalid records, and extreme outliers through defensive programming applications, analysis-based edit

checks, and other programmatic testing procedures. All findings will be forwarded to the project data manager for appropriate action and resolution.

## 7 STATISTICAL METHODS

### 7.1 General Methodology

Data will be analyzed by Precision for Medicine biostatistics personnel unless otherwise noted. Statistical analyses will be reported with tables, figures, and listings, presented in rich text format, and using recommended ICH numbering. Output specifications for all tables, figures, and listings will be in conformance with guidelines specified by the ICH in Appendix 7 of the *Electronic Common Technical Document Specification* (Apr 2003).

#### 7.1.1 Reporting Conventions

In general, all data collected and any derived data will be presented in subject data listings, for all enrolled subjects. Listings will be ordered by subject number and assessment or event date.

In general, continuous variables will be summarized to indicate the study population sample size (N), number of subjects with available data (n), mean, standard deviation, median, 25th (Q1) and 75th (Q3) quartiles, minimum, and maximum values. Categorical variables will be summarized by the population size (N), number of subjects with available data (n), number of subjects in each category, and the percentage of subjects in each category. Unless otherwise noted, the denominator to determine the percentage of subjects in each category will be based on the number of subjects with available data. Select ordinal data may be summarized using both descriptive statistics and counts and percentages of subjects in each category, as appropriate.

Non-zero percentages will be rounded to one decimal place. Rounding conventions for presentation of summary statistics will be based on the precision of the variable of summarization, as it is collected in its rawest form (ie, on the electronic Case Report Form [eCRF] or as provided within an external file) and are outlined as follows:

- The mean and median will be rounded to one more decimal place than the precision of the variable of summarization;
- Measures of variability (eg, standard deviation) will be rounded to two more decimal places than the precision of the variable of summarization; and
- Minimum and maximum values will be presented using the same precision as the variable of summarization.

Other statistics (eg, confidence intervals) will be presented using the same general rules outlined above, or assessed for the most appropriate presentation based on the underlying data.

### 7.1.2 *Summarization by Visit*

Data summarized by study visit will be based on the nominal, scheduled visit label as reported on the eCRF. Data will also be summarized separately for the last visit completed on study.

Data collected at unscheduled visits will not be included in by-visit summaries, but will be considered when endpoint derivations potentially include multiple visits (eg, determination of baseline value, determination of worst post-baseline value, etc.). All data will be included in subject listings.

### 7.1.3 *Data Handling Rules*

Unless otherwise noted, values reported as greater than or less than some quantifiable limit (eg, “< 1.0”) will be summarized with the sign suppressed in summary tables and figures, using the numeric value reported. Data will display on subject listings to include the sign.

### 7.1.4 *Standard Calculations*

Where appropriate, the calculated study day of each assessment or event will be presented with the assessment or event date on subject data listings, where study day will be determined as:

- The assessment/event date minus the date of study drug dosing, if the assessment/event date is prior to the date of study drug dosing; and
- The assessment/event date minus the date of study drug dosing, plus one, if the assessment/event date is on or after the date of study drug dosing.

Other variables requiring calculations will be derived using the following formulas:

- **Days:** A duration between two dates expressed in days will be calculated using the following conventions:
  - Later date – earlier date + 1, if the earlier date is on or after the date of study drug dosing; or
  - Later date – earlier date, if the earlier date is prior to the date of study drug dosing.
- **Months:** A duration expressed in months will be calculated by dividing the duration in days by (365.25 / 12);
- **Years:** A duration expressed in years will be calculated by dividing the duration in days by 365.25;

- **Change from Baseline:** Baseline is defined as the last available measurement taken prior to the first dose of either study drug. Change from baseline will be calculated as the post-baseline value minus the baseline value;
- **Percentage Change from Baseline:** Percentage change from baseline will be calculated as the change from baseline divided by the baseline value, multiplied by 100.

## 7.2 Analysis Populations

The analysis populations are defined as follows:

- **All Treated Population:** Includes all subjects who received any amount of either study drug.
- **Evaluable Analysis Set (EAS):** Includes all subjects who received any amount of either study drug and additionally who either have at least one evaluable response assessment or who discontinued the study for a reason of toxicity, clinical progression, or death.
- **Modified All Treated Population:** The protocol inclusion criteria require eligible subjects to be PD-L1 positive (defined as combined positive score [CPS]  $\geq 1$ ). If any subject with baseline CPS  $< 1$  were to be enrolled (a protocol deviation), then a Modified All Treated Population is defined as the All Treated Population excluding subjects with baseline CPS  $< 1$ .

Though subjects with baseline CPS  $< 1$  are not expected on study, if this were to occur, the Modified All Treated Population would be used for Efficacy summary analysis, rather than the All Treated Population. Otherwise, the All Treated Population will be used for both Efficacy and Safety analyses. Sensitivity analysis of efficacy on the EAS population will be presented only if there is a considerable difference between the EAS and the All Treated Population.

